### 3.6.2. Per-Protocol Analysis Set

The per-protocol analysis set will include mITT participants who have no protocol violations described below. In analyses performed on the per-protocol analysis set, participants will be analyzed according to actual treatment group (see [Section 3.2.2](#) for the definition). The detailed

definitions of protocol deviations, listed below, will be determined and documented prior to the Day 4 administrative database lock.

- Violation of eligibility criteria
  - Time to infusion post injury/last known normal (LKN) is more than 10 hours
  - Baseline contusion volume per investigator is  $\leq$  3 mL or missing
  - Baseline GCS is outside the range of 5-15
- Early discontinuation of treatment
  - Infusion is discontinued within 12 hours from the initiation of study drug infusion

### 3.6.3. Safety Analysis Set

The safety analysis of treated participants will include all randomized participants who received any infusion of study drug (BIIB093 3 mg/day, BIIB093 5 mg/day or the matching placebo). In analyses performed on the safety analysis set, participants will be analyzed according to their actual treatment groups (see [Section 3.2.2](#) for the definition), unless otherwise specified.

## 4. List of Planned Study Analyses

### 4.1. Interim Analysis

An interim analysis will be performed by an internal, independent, unblinded team when approximately 90 subjects are dosed and completed Hour 96 visit or terminated early, for administration purposes. The interim analysis will include all subjects who are in the mITT or safety population as described in the SAP. The interim analysis will include the following analyses:

- Demographic and baseline
- Exposure

- Efficacy – to include:
  - Change in total contusion volume at hours 24 and 96
  - GOS-E at hospital discharge, Day 30, Day 90 and Day 180
  - Change in hematoma volume at hours 24
  - Change in edema volume at hours 96
  - Change in total contusion volume by GOS-E by visit
- Safety – to include:
  - AEs/SAEs
  - Hypoglycemia
  - Laboratory
  - ECG

#### **4.2. Primary Analysis**

The primary analysis will be performed after the Day 4 (Hour 96) administrative database lock when the last participant completes their study drug infusion at the Hour 96 visit. The primary analysis is used to formally evaluate the treatment effect of BIIB093 on imaging-based endpoints as well as the on-treatment safety compared with the matching placebo. It will include the analyses of primary endpoint (change in total contusion volume as defined in [Section 3.4.1](#)) and other imaging-based endpoints, and on-treatment safety data summaries. The primary efficacy and safety analyses will be performed on the full analysis set and the safety analysis set, respectively, as defined in [Section 3.6](#), unless otherwise specified in [Section 5](#).

#### **4.3. Final Analysis**

The final analysis will be performed after the Day 180 final database lock. The final analysis is to formally evaluate the treatment effect of BIIB093 on functional and survival endpoints compared with the matching placebo. It will include all the secondary [REDACTED] endpoints not analyzed in the primary analysis, including functional, patient survival, neurocognitive, and patient-reported [REDACTED], as well as treatment requirement and [REDACTED]. The efficacy and safety analyses will be performed on the full analysis set and the safety analysis set, respectively, unless otherwise specified.

#### **4.4. Independent Data Monitoring Committee**

An independent data monitoring committee (IDMC) is established to assess the overall safety profile of BIIB093 during the study. The IDMC charter guides the overall governance plan for the IDMC. IDMC may recommend the Sponsor to terminate the study based on safety data. The IDMC will review the data every 3-5 months.

## 5. Statistical Methods for Planned Analyses

### 5.1. General Principles

Descriptive statistics will be provided for all efficacy endpoints. For continuous or numerical endpoints (change in volume, ██████████, GOS-E, etc.), number of participants with non-missing measures, mean, standard deviation (SD), median, quartiles (the 25th percentile or Q1, and the 75th percentile or Q3), and range (min, max) will be summarized. For categorical (nominal and ordinal) endpoints (GOS-E, mRS, etc.), number of participants with non-missing measures, number and percentage (%) of participants in each category of the endpoints will be summarized.

Treatment comparisons for the primary and secondary efficacy endpoints will be evaluated using 2-sided tests at the 0.05 level of significance. Point estimates of the treatment effect and 95% 2-sided confidence intervals (CIs) will be presented. The calculation of type I error will not adjust for multiple comparisons unless otherwise specified.

If more than 10% of data is missing for any baseline covariate, that covariate will not be used in the modeling described below.

All imaging efficacy endpoints including the primary endpoint will be evaluated by randomized treatment group using the full analysis set (the mITT participants; see [Section 3.6](#)), unless otherwise specified. The analyses performed on the full analysis set will be considered as the main analyses [[ICH E9 \(R1\) Addendum, 2020](#)].

The primary and secondary efficacy endpoints will also be analyzed based on the per-protocol analysis set as supplementary analyses. ██████████

██████████ The final model for each main analysis for the full analysis set will be used for the corresponding per-protocol analysis.

Subgroup analysis will be performed for primary and secondary efficacy endpoints and will present a point estimate of the treatment effect and 95% 2-sided CIs from unadjusted analyses, i.e., without including stratification factors or other covariates in the model other than the treatment group. These analyses will be performed on the full analysis set only. If the number of participants in a subgroup is too small (e.g. < 10% of mITT participants), the analysis in that subgroup may not be performed.

The software used for this analysis plan is SAS Studio.

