4. INTRODUCTION

4.1. Brain Contusion Background

Hemorrhagic lesions following trauma to the brain, which are referred to as contusions, may cause significant long-term morbidity and mortality. Bleeding into the brain parenchyma is problematic, due not only to the mass effect of a hematoma on intracranial pressure and associated brain herniation with compression of vital neurologic centers, but also to the neurotoxicity of hemoglobin [Kurland 2012].

In addition to the initial bleed following trauma, contusions often progress in size during the acute hospitalization period, significantly worsening prognosis. The delayed progression of bleeding into the brain is known as the hemorrhagic progression of contusion (HPC), or “blossoming” [Kurland 2012]. This expansion leads not only to an increase in hematoma volume, but also to the evolution of perihematomal edema surrounding the lesion itself. Both sequelae cause significant secondary brain injury. The prognosis for patients with traumatic brain injury (TBI) is often poor, with case fatality of up to 56%, and is worse for patients with HPC [O’Neil-Pirozzi 2018; Song 2016].

Progression of contusions are largely a function of the initial contusion volume, although other factors also contribute. Use of traditional and novel anticoagulants, antiplatelet agents, coagulopathy, age, and uncontrolled hypertension are all thought to contribute to some degree and are routinely controlled as part of clinical practice. Other processes that contribute to the progression of a contusion are analogous to the dysfunction of the cerebral microvasculature. Microvascular impairment, caused primarily by endothelial cell swelling and fragmentation, worsens hematoma expansion via the ongoing extravasation of blood into the brain parenchyma. In addition to ongoing bleeding, endothelial cell breakdown also permits the formation of perihematomal edema by extravasation of endovascular fluids into the brain’s interstitium. [Kurland 2012; Park 2008].

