16.2.2.2. Analysis of the Primary Endpoint

Primary analysis of the primary endpoint will compare BIIB093 (3 mg/day or 5 mg/day) and placebo groups using an ANCOVA (analysis of covariance) model, adjusting for covariates including all the stratification factors at randomization, 96 hours imaging modality (MRI vs NCCT) and baseline contusion volume per the central read. Multiple imputation will be used to account for the missing values for Hour 96.

Sensitivity analyses for the assumptions will be performed to evaluate the impact of analysis sets, the impact of missing data, and the intercurrent event handling. Details will be specified in the SAP.

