#### **3.4.1. Change in Total Contusion Volume (hematoma plus perihematomal edema) from Baseline to 96 Hours**

Total contusion volume will be assessed by the central imaging core laboratory on baseline NCCT, 24-hour NCCT, and the 96-hour scan (MRI and / or NCCT) and the scans obtained prior to DC, IPH evacuation or CMO. Change in total contusion volume (hematoma plus perihematomal edema) as measured by brain imaging from baseline to 96 hours or prior to DC, IPH evacuation, or CMO if these procedures occur before 96 hours per central review, will be derived from available central reads, at baseline (before Hour 0) and closest to Hour 96. If multiple timepoints

are applicable, the read from the visit closer to Hour 96 will be used for analysis. If both MRI and NCCT have been carried out then the MRI read will be used.

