### **5.3.2. Baseline Disease Characteristics per CRFs**

- Time (hours) to randomization post injury or LKN
- Time (hours) to initiation of study drug infusion post injury or LKN
- Time (hours) to NCCT for eligibility post injury or LKN
- Time (hours) to initiation of study drug infusion from NCCT for eligibility
- Injury types
- Baseline GCS before randomization
- Total injury severity scoring (ISS) score excluding head or face
- Baseline brain contusion volume (mL) per investigator
- Baseline brain contusion volume (mL) per the central review
- Baseline hematoma volume (mL) per the central review
- Baseline edema volume (mL) per the central review
- Baseline blood glucose
- Baseline alcohol level
- Baseline sodium

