### 5.6.1. General Analysis Methods for Efficacy Endpoints

All endpoint models (binary logistic regression, ordinal logistic regression, Cox model, and analysis of covariance) below will regress the outcome on the randomized treatment group, comparing the BIIB093 combined with placebo groups, adjusting for all the IRT stratification factors at randomization (see [Section 3.5.1](#)), baseline contusion volume per the central review and baseline GCS.

Analysis of covariance (ANCOVA) will be performed to compare the change in total contusion volume (primary analysis), change in absolute hematoma volume, the change in absolute edema volume, [REDACTED] from baseline in the main analysis comparing the BIIB093 combined with placebo groups. The least square (LS) mean difference with the corresponding 2-sided 95% CI and p-values for the treatment group will be provided.

Binary logistic regression will be used for binary outcomes comparing the BIIB093 combined with placebo groups. Odds ratio, the corresponding 2-sided 95% confidence interval (CI) and p-value will be reported for the treatment group.

Ordinal logistic regression (proportional odds model) will be used for GOS-E as a 7-category ordinal scale (1/2, 3, 4, 5, 6, 7, 8) and for mRS as a 5-category ordinal scale (0/1, 2, 3, 4, 5/6) at Day 90 and 180. Odds ratio, the corresponding 2-sided 95% CI and p-value for the treatment group will be reported.

The proportional odds ratio assumption will be tested using likelihood ratio test based on observed data. In the case the assumption does not hold (p-value < 0.05) or non-convergence, the Mann-Whitney test will be used as the primary inference and the source of non-proportionality or non-convergence will be investigated. Following the Mann-Whitney test, dichotomized analysis will be conducted to assess the treatment effects.

The Cox proportional hazard model will be used to assess the treatment effect on overall survival at Day 90 for all randomized participants. Hazard ratio, 2-sided 95% CI as well as the p-value for the treatment group will be reported. Kaplan-Meier curves will be presented by randomized treatment group, and Greenwood's formula will be used to calculate the standard error of the Kaplan-Meier estimates.

Multiplicity will be not be adjusted for the tests of the primary and secondary endpoints, since the current study sample size is not powered for a moderate treatment effect on GOS-E.

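### Subgroup estimates use treatment-only models although the main models adjust for baseline contusion volume; this gives up some precision in exploratory analyses

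*SAP*

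**What the plan says.** SAP 5.1 applies one rule to all subgroup analyses of the primary and secondary efficacy endpoints. They report "a point estimate of the treatment effect and 95% 2-sided CIs from unadjusted analyses", and the models are fitted "without including stratification factors or other covariates in the model other than the treatment group". The SAP gives no reason for this. A subgroup may be skipped if it is too small, with under 10% of the mITT participants as the example. I found no adjusted subgroup model and no treatment-by-subgroup interaction in the visible text.

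The main models are different. SAP 5.6.1 adjusts every endpoint model for the IRT stratification factors, "baseline contusion volume per the central review and baseline GCS". Protocol 16.2.2.2 adjusts the primary endpoint for the stratification factors, "96 hours imaging modality (MRI vs NCCT) and baseline contusion volume per the central read". Modality therefore appears in the protocol's list but not in the SAP's.

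On prognosis, Protocol 4.1 states: "Progression of contusions are largely a function of the initial contusion volume". The same sentence adds that other factors contribute, and it gives no share of variance explained.

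The covariate is available. SAP 5.3.2 lists "Baseline brain contusion volume (mL) per the central review" among the baseline characteristics. The modality of the Hour 96 read is also known, because SAP 3.4.1 has to choose between scans: "If both MRI and NCCT have been carried out then the MRI read will be used".

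**The concern.** The plan adjusts for baseline volume in the full mITT set, where chance imbalance is smallest, and drops it in the subgroups, where chance imbalance is largest. If volume is as prognostic as the protocol says, part of the spread in each subgroup estimate is removable noise.

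Two things are at stake. For the volume endpoints, subgroup intervals are wider than the collected data require. For GOS-E, mRS, delayed intubation and survival, the subgroup tables show unadjusted odds or hazard ratios beside an adjusted overall ratio. Those ratios are non-collapsible, so the two can differ even when the treatment effect is the same in every subgroup.

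**Working it through.** **Inputs**
- SD of change 29 mL, difference 15 mL, 80 v 80, two-sided 5%, about 90% power: Protocol 16.8 and SAP 2.3.
- 1:1 pooled active to pooled placebo, from the 1:1:1:1 allocation: Protocol 9.2.
- Smallest subgroup that need not be dropped: about 10% of mITT (SAP 5.1). If all 160 were in mITT, that is about 16, or 8 v 8.
- R², the share of outcome variance explained by the covariates: not in the documents. I assume 0.1 and 0.3 as the working range and 0.5 as an extreme.

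**Step 1: the plan's own figure.** SE = 29 × √(2/80) = 4.59 mL, and 15/4.59 = 3.27. Normal approximation: Φ(3.27 − 1.96) = 90.5%. The noncentral t with 158 df gives 90.2%. The stated power reproduces.

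**Step 2: precision in subgroups.** SE = 29 × √(2/n) × √(1 − R²), with n per group. The 95% half-width is SE × t(0.975), with 2n − 2 df unadjusted and 2n − 3 df with one covariate.

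| Per group | SE, unadjusted | SE, R² 0.1 | SE, R² 0.3 | Half-width, unadjusted | Half-width, R² 0.1 | Half-width, R² 0.3 |
|---|---|---|---|---|---|---|
| 40 | 6.5 | 6.2 | 5.4 | 12.9 | 12.2 | 10.8 |
| 20 | 9.2 | 8.7 | 7.7 | 18.6 | 17.6 | 15.5 |
| 8 | 14.5 | 13.8 | 12.1 | 31.1 | 29.7 | 26.2 |

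All entries are in mL. Adjustment multiplies the SE by √(1 − R²), which is 0.95 at R² 0.1 and 0.84 at 0.3. That is worth the same as 1/(1 − R²) = 1.11 or 1.43 times the participants.

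**Step 3: chance imbalance.** Under simple randomisation, covariate imbalance shifts an unadjusted estimate with SD = 29 × √R² × √(2/n).
- 20 per group: 2.9 mL (R² 0.1) to 5.0 mL (R² 0.3).
- 40 per group: 2.1 to 3.6 mL.
- 8 per group: 4.6 to 7.9 mL, and 10.3 mL at R² 0.5.

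At 20 per group, a 15 mL shift would need an imbalance of 15/5.0 = 3.0 SD at R² 0.3, or 15/2.9 = 5.2 SD at R² 0.1.

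**Step 4: does the unadjusted interval allow for this?** Yes. At 20 per group and R² 0.3, 7.67² + 5.02² = 58.8 + 25.2 = 84.0, which is 9.17² = 84.1 up to rounding. The unadjusted variance is the adjusted variance plus the imbalance variance, so the interval is wide but has its nominal coverage.

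**Step 5: modality.** The documents give no size for the MRI-NCCT difference. If it is assumed to be 5 to 15 mL, a 20-point difference between arms in MRI share moves the estimate by 0.20 × 5 = 1 mL to 0.20 × 15 = 3 mL.

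**The case against.** The strongest defence is that nothing here is wrong in the sense of bias. Within a randomised subgroup the unadjusted mean difference is unbiased, and its interval covers as stated. For the volume endpoints it targets the same quantity as the ANCOVA difference. All of that stands.

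The gain is also modest. At 20 per group and R² 0.3 the half-width is still 15.5 mL, about the whole assumed effect. Stratification by volume class and GCS, and subgroups defined by volume class, already limit imbalance somewhat, although two broad classes leave variation in volume within each. In very small subgroups, multi-covariate models for delayed intubation, death or a 7-level GOS-E may not fit stably, so a simple rule there is defensible. Finally, modality is set after randomisation and depends partly on whether the participant can have an MRI, so it is not a baseline covariate like volume.

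A reader might infer more than the documents support:
- **That the rule creates false subgroup signals.** It does not. Step 4 shows the interval already carries the imbalance variance.
- **That imbalance in either volume or modality can match the 15 mL effect.** For modality the shift is about 1 to 3 mL under the stated assumptions. For volume it takes at least 3 SD at 20 per group, and only the 8 v 8 case with R² 0.5 has an SD near 10 mL.
- **That subgroup results will steer the Phase 3 population.** No passage says so. Protocol 16.7 links the interim analysis only to accelerated Phase 3 preparation, and the interim list in SAP 4.1 contains no subgroup analysis.

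None of this gives a reason to omit one continuous, recorded, prognostic covariate from a linear model for volume change.

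**Conclusion.** The point holds as a minor one. For the volume endpoints, the treatment-only rule discards a covariate that the main analysis uses, at a cost in subgroup standard error of about 5% (R² 0.1) to 16% (R² 0.3), measured as the reduction that adjustment would bring. For the ratio endpoints the cost is comparability with the overall estimate, and how much can be done depends on subgroup size and event counts.

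The size rests on the planning SD of 29 mL, an even split within each subgroup, and assumed R² values. The calculation ignores missing scans and mITT exclusions, so actual intervals would be wider. The subgroup results are estimates with intervals and are not declared confirmatory. The primary test, its power and the sample size are unaffected.

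**What to change.** Amend the subgroup paragraph of SAP 5.1, preferably before anyone sees unblinded subgroup data:

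1. **Volume endpoints.** Replace the treatment-only rule with ANCOVA containing treatment and continuous central baseline contusion volume. Fit it within each subgroup, or as one model with subgroup and treatment-by-subgroup terms. Keep the unadjusted results as supportive.
2. **Hour 96 modality.** First reconcile Protocol 16.2.2.2, which includes it, with SAP 5.6.1, which does not. Then treat it in the Hour 96 volume subgroups as the reconciled main model does, bearing in mind that it is set after randomisation.
3. **Functional, intubation and survival endpoints.** Adjust for baseline volume and GCS only where subgroup size and event counts allow a stable fit, and state that criterion in advance. Elsewhere report the unadjusted ratio, with a note that it is not directly comparable with the adjusted overall ratio.

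The cost is a few sentences in the SAP and some extra programming. No new data are needed.

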#### 5.1.1. Handling of Missing Date/time in Concomitant Medications

Missing start and/or stop date/time will be handled as follows for defining concomitant use of therapies. If study treatment start date/time is not available, the date/time of randomization will be used.

- If both start and stop date/time of a therapy are missing, that therapy is considered concomitant.

- If the start date/time of a therapy is missing and the stop date/time of that therapy falls on or after the date/time of the study treatment start date/time, that therapy is considered concomitant.
- If the start date/time of a therapy is prior to the date/time of the study treatment start date/time and the stop date/time of that therapy is missing and the therapy is listed as continuing, that therapy is considered concomitant.
- If the start date/time of a therapy is prior to the date/time of the study treatment start date/time and the stop date/time of that therapy is missing and the therapy is listed as not continuing, that therapy is considered not concomitant.

### **5.1.2. Handling of Missing Date/Time in Adverse Events**

Missing start/stop date/time will be handled as follows for defining treatment-emergent events. If study treatment start date/time is not available, the date/time of randomization will be used.

- If both the start and stop dates/time for an event are missing, then that event is considered treatment-emergent.
- If the start date/time for an event is missing and the stop date/time fall after the start date/time of the study treatment, then that event is considered treatment-emergent.
- If the start date was the same as the start date of the study treatment and the start time was missing, and the stop date/time is after the date/time of the study treatment or cannot be compared with the date/time of study treatment, then that event is considered treatment-emergent.

### **5.1.3. Handling of Partial Date/Time in Concomitant Medications and Adverse Events**

For a therapy or an adverse event with a partial start and/or end date/time, the year/month/day of the therapy start and/or end will be compared to those of the first dosing date/time of the study treatment to determine the imputation rules. If a participant is not dosed, the date/time of randomization will be used.

The last date/time on study will be taken as the last visit/evaluation date/time from all available data for the participant. If a participant died during the study, the last date/time on study will be the date/time of death.

- For the start date/time of AEs or concomitant medications,
  - If only time is missing, and that the AE/concomitant medication starts on the same day as the treatment (or randomization if the participant is not dosed), then impute missing time using the treatment start time (study Hour 0); otherwise use the first (01) hour of that day as the hour.
  - If only day is missing, and that the AE/concomitant medication starts in the same month as the treatment (or randomization if the participant is not dosed), then impute missing day using the treatment start date (study Day 1); otherwise use the first (01) day of that month as the day.

- If both day and month are missing, and that the AE/concomitant medication starts in the same year as the treatment (or randomization), then impute missing day and month using the treatment start date (Study Day 1); otherwise, use January 01 (01JAN) as the day and month.
- If the date/time for AE/concomitant medication is completely missing (no day, month or year), the start date/time of the study treatment will be used.
- For the stop date/time of AEs or concomitant medications,
  - If only time is missing, and that the AE/concomitant medication stops on the same day as the treatment, then impute missing time using the treatment end time; otherwise use the last (23) hour of that day as the hour.
  - If only day is missing, and that the AE/ concomitant medication stops in the same month as the treatment, then impute missing day using the treatment end date; otherwise use the last day of that month as the day.
  - If both day and month are missing, and that the AE/concomitant medication stops in the same year as the treatment, then impute missing day and month using the treatment end date; otherwise, use December 31 (31DEC) as the day and month.
  - If the stop date is completely missing (no day, month or year), the study end date/time will be used.

